2.1 Phase I

In Phase I, all participants will be given access to the SHUTi intervention. Phase I will assess the feasibility and acceptability of the intervention and ensure that our data collection processes are functioning as they should be. As data become available to the research team, we will assess patterns based on participant feedback and may make modifications to the program. If this is the case, we will amend the protocol prior to beginning Phase II. Participants will receive training from a member of the research team on accessing the program and using the handheld tablets provided as part of study participation. Individuals who participate in Phase I of this study and are re-admitted to 1SE will not be eligible for participation in Phase II, as they will have already experienced the intervention.

2.2 Phase II

Randomization will be achieved using a random number generator, assigning equal numbers of participants to each of the two conditions. The PI and AIs will remain blind to the randomization scheme until each study participant is deemed eligible and signs the consent form.

Intervention/control groups (Phase II only)**:

1. **Intervention group:** 6 sessions (“modules”) of SHUTi intervention (at least one module completed while inpatient, the rest while outpatient): In SHUTi, customization is based on multiple variables, including sleep diary responses. The SHUTi program tailors specific recommendations based on sleep diary responses or other input within the program (e.g., responses on the Dysfunctional Beliefs and Attitude Scale trigger recommendations for specific cognitive restructuring strategies).
2. **Control group:** education/monitor only (insomnia education web-based program that participants access and read at their own pace – contains no customization of program based on sleep diary responses). Participants in the control group are given educational information (like they might see on WebMD or National Sleep Foundation websites), but are left to apply it themselves.

**Participants who are randomly assigned to the intervention condition will be granted access to the program free of charge for up to six months from the start of the program. Participants who are randomly assigned to the education-only condition will be given access to the full SHUTi program three months after discharge upon request. Similarly, participants who are randomly assigned to the intervention condition will be granted access to the education materials provided to the education-only condition participants three months after discharge upon request.

All participants enrolled in this study will first be admitted under the screening and assessment protocol on the 1SE clinic (14-AA-0181), which includes adults at least 18 years of age seeking treatment for alcohol use disorders. Once consented and enrolled into the inpatient treatment, screening, and research protocol, participants are screened and recruited enrollment in additional studies for which they meet eligibility criteria (including the study described herein). Study participants will be asked to

Protocol Number: 18-CC-0079

come back to the Clinical Center post-discharge for a follow-up visit to complete a face-to-face semi-structured interview (Phase I participants only) and questionnaires (Phases I and II participants). If participants are unable to return for the follow-up visit, we will attempt to conduct the surveys and interview via phone.

2.3 Screening Measures

Insomnia Severity Index (ISI). The ISI is a seven-item global index of self-reported insomnia symptom severity. Seyffert and colleagues (2016) categorized insomnia severity by scores as follows: 0-7 = no clinically significant insomnia, 8-14 = subthreshold insomnia, 15-21 = moderate insomnia, and 22-28 = severe insomnia. The Veterans' Administration (VA) is currently using this questionnaire as a clinical assessment tool to provide VA healthcare providers information about their patients' sleeping difficulty and its effects on daytime functioning (Veterans Administration, 2017). We will be using the ISI to determine if potential participants are eligible to be enrolled in this study and will only consider individuals with an ISI score ≥ 10 for inclusion in the study.

Objective measure of Apnea Hypopnea Index (presence/severity of obstructive sleep apnea): the WatchPAT. We will utilize the WatchPAT, which is a portable diagnostic medical device, to detect presence/severity of obstructive sleep apnea (OSA). The research participant will wear the WatchPAT on his or her wrist and finger when he or she goes to bed at night for one night during their inpatient stay as part of the screening prior to randomization. The WatchPAT works by using a Peripheral Arterial Tone (PAT) technology that allows for non-invasive and portable detection of sleep apnea. The data collected from the WatchPAT will be uploaded into a proprietary computer software program which uses validated algorithms to analyze two indices, Apnea-Hypopnea Index (AHI) and Respiratory Disturbance Index (RDI), to determine the total Apnea Hypopnea Index and provide an indication of presence and severity of sleep apnea. While polysomnography remains the "gold standard" diagnostic tool, clinical studies have shown that the WatchPAT has a high degree of correlation with polysomnography studies ($r = 0.85-0.96$) in detecting respiratory events during sleep (Itamar Medical, 2016). Interpretation of the WatchPAT results will be supervised by a physician at the University of Pennsylvania with expertise in sleep medicine ([name], who is also an AI on the study). If a participant has more than 15 "events" per hour of sleep, they will be ineligible for participation in the study. The results of the WatchPAT study will be reviewed with the patient and the clinical care team. If the patient is seen to have mild obstructive sleep apnea (5-14.9 events/hour of sleep), we will recommend him/her to work on losing weight (if they are overweight or obese), avoid alcohol use, and follow up with a primary care provider. In the case that they are found to have moderate to severe OSA (score of 15 or higher), we will provide the patient with a patient education handout that explains what OSA is, the risks associated with untreated OSA, and the treatment options available. We will urge the patient to seek evaluation and treatment through a primary care provider or directly from a sleep medicine clinic, as is appropriate for them.

2.4 Study Measures

Feasibility and acceptability measures. Participants enrolled during Phase I will be asked to start the SHUTi modules prior to being discharged from inpatient treatment. They will be invited to participate in a short interview after they complete the first SHUTi module in order to gather additional information on program delivery and acceptability in the population. We will also utilize the Internet Evaluation and Utility Questionnaire (Ritterband et al., 2008) at the pre-discharge interview, which is a 16-item measure

Protocol Number: 18-CC-0079

designed to assess usability, likeability, usefulness, understandability, and convenience of the intervention. We will also implement an exit assessment for Phase I *and* II participants. At the exit assessment, we will use the Internet Impact and Effectiveness Questionnaire, the Internet Evaluation and Utility Questionnaire, and the Internet Intervention Adherence Questionnaire (Ritterband et al., 2008). The Intervention Impact and Effectiveness Questionnaire is a 14-item measure designed to assess perceptions of the impact of the program. Responses on all questionnaires related to utility and impact are rated on 5-point Likert scales from 0 (“not at all”) to 4 (“very”). Participants will complete these assessments with a member of the research team who will take notes on participants’ comments for each question. Open-ended questions (used in Phase I only) will be audio recorded and the entire session (including the questionnaires) are expected to last between 20-60 minutes, depending on the participant's responses. Additional measures of program adherence (in the experimental group, for both Phases I and II) will be measured by three variables: login count (goal of two per week), completed diary count (minimum of five per week), and number of “cores” completed out of a possible six cores.

Insomnia Severity Index (ISI). The ISI is a seven-item global index of self-reported insomnia symptom severity. It is valid, reliable, sensitive to changes in insomnia treatment (Bastien, Vallieres, & Morin, 2001; Morin, Belleville, Belanger, & Ivers, 2011) and validated for online use (Thorndike et al., 2011). Seyffert and colleagues (2016) categorized insomnia severity by scores as follows: 0-7 = no clinically significant insomnia, 8-14 = subthreshold insomnia, 15-21 = moderate insomnia, and 22-28 = severe insomnia. Changes in the ISI over time will be a primary outcome measure. The ISI is collected within the SHUTi intervention program at the beginning of each core, but participants in both Phase I and Phase II will also complete a paper version of the ISI during the pre-, mid-point, and post-test assessments.

Daily sleep and symptom diaries. Prospectively collected sleep diaries are a proven method for assessing insomnia and track treatment effects (Carney, et al., 2012; Buysse, Ancoli-Israel, Edinger, Lichstein, & Morin, 2006) and have been used for other sleep studies among patients on 1SE (inpatient and outpatient). Participants will be asked to complete at least five out of every seven days of daily sleep and symptom diaries. These diaries will include sleep/wake times, time in bed, sleep onset latency, number and duration of awakenings, sleep quality, naps, alcohol consumption, any over-the-counter or prescription medications used to help with sleep (participants will be instructed to include any marijuana use in this section), and open-ended comments. For the experimental group, diaries will be used to assess adherence to their “sleep window,” based on actual time in bed as a proportion of prescribed time in bed. We will cross-validate diary-reported sleep duration with actigraphy data when possible. Secondary outcome measures captured in the diaries will include a categorical measure of relapse (i.e. whether the participant reports any drinking post-discharge) as well as quantity and frequency of drinking, which will be calculated in the case of relapse, as well as all other diary variables.

Penn Alcohol Craving Scale (PACS). The PACS is a clinical tool for practitioners to measure alcohol craving. It is a five-item self-administered instrument that measures frequency, intensity, and duration of thoughts about drinking along with ability to resist drinking. The final item asks the responder to provide an average rating of his or her craving over the course of the past week. The PACS has excellent internal consistency (Cronbach's $\alpha = 0.92$). Construct, predictive, and discriminant validity has also been established. This assessment takes between two and five minutes to complete (Flannery, Volpicelli, & Pettinati, 1999). The PACS will be administered as part of the post-test assessment.

Functional Outcomes of Sleep Questionnaire (FOSQ-10). The FOSQ-10 is a 10-item abbreviated version of the original 30 item instrument used to evaluate quality of life in relation to daytime sleepiness. The 30-

Protocol Number: 18-CC-0079

item questionnaire measures difficulty in performing tasks from five domains due to sleepiness or tiredness: General Productivity, Activity Level, Vigilance, Social Outcome, and Intimacy and Sexual Relationships (Weaver et al., 1997). The FOSQ-10 consists of two questions from General Productivity subscale, three from Activity Level, three from Vigilance, and one each from Social Outcome and the Intimacy and Sexual Relationships subscales. The 10-item version demonstrates high internal consistency similar to that of the original instrument (Cronbach's $\alpha = 0.87$), high correlation with the 30-item version of the scale, and the ability to detect a wide range of functional limitations (Chasens, Kampman, & Weaver, 2009). To obtain the total score for the FOSQ-10, the mean-weighted item score is calculated for each subscale. These subscale scores are then averaged and the mean was multiplied by five. Lower scores are indicative of higher levels of dysfunction. The FOSQ-10 will be administered at pre- and post-test time points.

Objective measure of sleep: actigraphy. "Actiwatches" are small wristband data loggers that record digitally-integrated measures of gross motor activity. These devices contain accelerometers and light sensors in order to objectively assess sleep. Prior studies have demonstrated actigraphy's high sensitivity with moderate accuracy for detecting sleep in populations with normal and disturbed sleep when compared to polysomnography (Kushida et al., 2001; Paquet et al., 2007). The *Actiwatch Spectrum Plus* (Philips Respironics) has been used in previous studies with patients on 1SE in both inpatient and outpatient settings. The watch is worn on the non-dominant wrist. Study participants will be asked to wear an actiwatch for 4 days, 3 nights (Phase I only) and for at least 1 week (Phase II only) at three study time points (Pre SHUT-i®/Education-Only initiation, 3-4 weeks after SHUT-i®/Education-Only initiation and Post SHUT-i®/Education-Only program completion). Participants will return the actiwatches either in person (if the participant will be returning to the Clinical Center) or by mail after each study time point so that the research team can download the data and return the watch to the participant (with the exception of the last study time point). The main outcome of interest will be improvements in sleep efficiency from baseline to follow-up assessment periods. The watch also provides measures of total sleep time (TST), wake after sleep onset (WASO), sleep onset latency (SOL), number of awakenings (NWAK), and time in bed (TIB).

Pittsburgh Sleep Quality Index (PSQI). The Pittsburgh Sleep Quality Index (PSQI) is a 19-item, self-rated questionnaire used to measure sleep quality and disturbances over a 30-day time interval. Nineteen individual items generate seven "component" scores: subjective sleep quality, sleep latency, sleep duration, habitual sleep efficiency, sleep disturbances, use of sleeping medication, and daytime dysfunction. A global summation score of five or higher is indicative of poor sleep quality (Buysse, Reynolds, Monk, Berman, & Kupfer, 1989). The PSQI has been validated in populations with insomnia and other sleep disorders, with psychiatric patients, and in normal populations (Backhaus, Junghanns, Brooks, Riemann, & Hohagen, 2002; Doi, Minowa, Uchiyama, Okawa, Kim, Shibui, & Kamei, 2000). There exists some early evidence of validity in alcohol-dependent populations (Brooks, Krumlauf, Whiting, Clark, & Wallen, 2012; Wallen et al., 2014). The PSQI has internal consistency and a reliability coefficient ranging from 0.80 to 0.83 for its seven components (Buysee, et al., 1989; Carpenter & Andrykowski, 1998). It takes approximately five minutes to complete. Phase I and II participants will complete the PSQI at the pre- mid-point, and post-test.

The Multidimensional Fatigue Symptom Inventory-Short Form (MFSI-SF). The MFSI-SF (Stein 2004), which is a 30-item measure, was used in the 2012 study by Ritterband and colleagues that demonstrated the efficacy of internet-delivered CBT-I for cancer survivors. This measure has also been used in relation to insomnia and internet-based delivery of CBT-I by Thorndike and colleagues in 2013. A

Protocol Number: 18-CC-0079

review by Donovan and colleagues (2015) reported that the measure has been used in a variety of study designs, including longitudinal, cross-sectional, and randomized control trials, with acceptable psychometric properties.

Epworth Sleepiness Scale (ESS). The Epworth Sleepiness Scale (ESS) is an eight-item self-administered questionnaire that provides a measure of an individual's general level of excessive daytime sleepiness over a one week time period (Johns, 1991). Individuals are asked to rate their usual chances of dozing off or falling asleep on a four-point scale in eight distinct situations or activities that most people engage in during their daily lives. Higher scores are indicative of higher levels of daytime sleepiness. An alpha coefficient between 0.70 to 0.88 has been documented and numerous studies support high validity and reliability (Spira, Beaudreau, Stone, et al., 2012; Johns, 1992). A score higher than ten is indicative of excessive daytime sleepiness (Johns, 1993). Completing the ESS generally takes two to three minutes.

Self-Efficacy for Sleep Scale (SE-S). The SE-S includes nine items used to measure the level of confidence a person has in performing behaviors that might be helpful in initiating sleep. Each item is scored on a five-point Likert scale from 1 representing "not confident" to 5 representing "very confident." The total score ranges from nine to 45, with higher scores indicative of greater confidence. Concurrent validity of the scale was established by comparison with PSQI, sleep diaries, and objective measures of sleep (Edinger, Wohlgemuth, Radtke, Coffman, & Carney, 2007). The scale has excellent internal reliability (Cronbach's alpha of 0.71-0.86; Edinger, et al., 2007; Rutledge, La Guardia, & Bluestein, 2013). Test-retest reliability has also been established (Fichten, Libman, Creti, Amsel, Sabourin, Brender, & Bailes, 2001). The SE-S was shown to be a significant predictor of sleep quality (unpublished data); increased self-efficacy for sleep was associated with better sleep quality (Brooks et al., unpublished data).

Dysfunctional Beliefs and Attitudes about Sleep (brief version; DBAS-16). The DBAS-16 is a 16-item questionnaire that assesses sleep-related cognitions including faulty beliefs and appraisals, unrealistic expectations, and perceptual and attention bias. The DBAS-16 has adequate internal consistency (Cronbach's alpha = 0.77 for clinical and 0.79 for research samples) and temporal stability ($r = 0.83$). Factor structure is similar to the original 30-item version of the questionnaire and includes perceived consequences of insomnia, worry/helplessness about insomnia, sleep expectations, and medication. Domains include expectations about sleep requirements and issues with being worried or feeling helpless about insomnia (Morin, Vallieres, & Ivers, 2007). The scoring of the DBAS-16 is the average score of all items.

Inventory of Depressive Symptoms (IDS; 30-item self-rated version). The IDS is a 30 item measure that can be used to screen for depression or measures symptom severity using the nine symptom domains used to define a major depressive episode. The IDS has high internal consistency (Cronbach's alpha = 0.90; Trivedi et al., 2004). Administration of the IDS takes approximately 10-15 minutes and scores are calculated by summing responses the 28 of the items for a score ranging from 0 to 84. A higher score indicates higher severity of depressive symptoms, with 49-84 indicating very severe symptoms (Rush et al, 2003, Trivedi et al, 2004).

Trait Anxiety Inventory. The Trait Anxiety Inventory is a 20-item measure of anxiety (Spielberger et al., 1983). The Trait Anxiety Inventory differs from the State Anxiety Inventory by asking questions on how respondents "generally feel" (Trait Anxiety), while the State Anxiety questionnaire asks how respondents feel "at this moment." Responses to each statement is rated on a four point scale, ranging from "almost never" to "almost always". The Trait Anxiety Inventory demonstrates high internal

Protocol Number: 18-CC-0079

consistency (Cronbach's alpha > 0.86) (Barnes, Harp, & Jung, 2002). Higher scores on the STAI indicates higher levels of anxiety.

Composite Scale of Morningness (CSM). The Composite Scale of Morningness is a 13-item scale (Smith, Reilly, & Midkiff 1989). Questions address topics like morning affect, preferred sleep/wake times, and peak cognitive performance, with scores ranging from 13 (reflecting "eveningness") to 55 (reflecting "morningness"). The CSM typically shows relatively high internal consistency (Cronbach's alpha > 0.8) (Di Milia, Adan, Natale, & Randler 2013).

We will pull additional data from the screening/treatment protocol to characterize our sample and conduct exploratory analysis based on the aforementioned aims, including but not limited to:

- Childhood Trauma Questionnaire (CTQ)
- Structured Clinical Interview for Diagnostic and Statistical Manual of Mental Disorders (DSM-IV or DSM-5) (SCID)
- Clinical Institute Withdrawal Assessment – Alcohol revised (CIWA-Ar)
- Comprehensive Psychopathological Rating Scale (CPRS)

[figure not shown]

Figure 1: Study flow chart

Participants will be screened for eligibility on or after day 14 of inpatient treatment. Days 14-21 will be when the participant is consented, screened for OSA (after consent), randomized (if they meet inclusion requirements), and begin daily diary assessments as a baseline measure. If they are discharged before they are deemed eligible for continue study participation and randomized to a group, they will be removed from the study.

Table of Measures						
	Inpatient			Outpatient		
	Pre-Test (Before SHUT-i® Intervention or Education only program initiation)	Start SHUT-i® Intervention or Education only program	Prior to or within 2 weeks of Discharge	3-4 weeks after SHUT-i® Intervention or Education only program initiation	Post-Test (After SHUT-i® Intervention or Education only program completion)	6-7 months post-discharge (clinic visit or by phone)
ISI				X		X
PACS					X	X
PSQI	X			X	X	
DBAS-16	X				X	
FOSQ-10	X				X	
SE-S	X				X	
IDS	X				X	
ESS	X				X	
Trait Anxiety Inventory	X				X	
CSM	X					
MFSI-SF	X				X	
At least 4 days, 3 nights (Phase I)/1 week (Phase II) of actigraphy assessment	X			X	X	
Sleep Diaries	X			X	X	
Start SHUTi (Phase I and II) or education only (Phase II only) program		X				
Abbreviated Internet Evaluation and Utility Questionnaire (Phase I only)			X			

Protocol Number: 18-CC-0079

Internet Impact and Effectiveness Questionnaire, Internet Evaluation and Utility Questionnaire, and the Internet Intervention Adherence Questionnaire (Phase I and II)					X	
Exit interview regarding experience with SHUTi program (Phase I only)					X	
Dichotomous Yes/No Relapse Assessment						X (If YES, TLFB will be administered)
TLFB						X

Protocol Number: 18-CC-0079

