Cocaine is a stimulant that can disrupt sleep and sleep architecture in both humans and animals (Angarita, Emadi, Hodges, & Morgan, 2016; Cortes et al., 2016; Irwin, Bjurstrom, & Olmstead, 2016). Increased arousal is the most common effect of cocaine use with regards to sleep and animal models showed that the level of arousal is dose dependent (Chakravorty, Vandrey, He, & Stein, 2018; Cortes et al., 2016). Individuals who are diagnosed with cocaine use disorder (CoUD) have an underlying sleep disturbance that may persist even after abstinence for several weeks, although recent evidence suggests that improving sleep may increase the likelihood of sustained abstinence from cocaine (Angarita et al., 2016; Hodges, Pittman, & Morgan, 2017; Winhusen, Theobald, & Lewis, 2019). CoUD as well as other substance use disorders are commonly comorbid with AUD (Chakravorty et al., 2018). For this study, we will only exclude participants who meet the DSM-5 criteria for severe CoUD. During analysis, we will attempt to control for any comorbid substance use disorders.

Opioids are associated with a more complex picture of sleep disorders that includes insomnia, obstructive sleep apnea, and complex sleep apnea (Hassamal, Miotto, Wang, & Saxon, 2016). Patients who are diagnosed with opioid use disorder are usually treated with oral naltrexone. "Oral naltrexone is capable of inducing fatigue, nausea, sleepiness, restlessness, and dysphoria in nonopiate users during the first few hours acutely post-ingestion" (Mysels, Cheng, Nunes, & Sullivan, 2011, p.22). Insomnia also transiently worsened with naltrexone treatment, but it is purported to be associated with subacute opiate withdrawal (Mysels et al., 2011). Thus, we are excluding participants who meet the SCID-5/DSM-5 criteria for opioid use disorder regardless of severity.

A previous study on predictors of dropout in a CBT-I program indicated a drop-out rate of around 34%. Based on potential dropout of those individuals who are eligible and are randomized in Phase II (conservative estimate: 40%), and a target of 20 individuals per group, we have adjusted our accrual ceiling to 67 (plus 12 for Phase I). We will submit an amendment to adjust this number if we discover the prevalence and severity of OSA in the population is higher than our estimate based on results from the WatchPAT screening.

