Phase II: 60 participants - the total sample size for phase II of this study will test the primary hypotheses associated with the analysis plan. With insomnia severity as the primary outcome, we will use a two-sided alternative hypothesis that the rate of change will be different between the intervention group and the control group. Assuming a correlation of 0.6 between the two time points, an alpha level of 0.05, a power level of 0.8, and an estimated attrition rate of 40 percent, we will be able to detect an effect size of 0.84 with 60 participants (Fitzmaurice, Laird, & Ware, 2012). Permuted block randomization with block size of four will be used to equally assign participants in each group. The statistician, who will not have any contact with participants, will prepare the randomization sequences and give out the allocation assignment after each participant is consented.

Mixed model for repeated measure with group, time, and the interaction of group by time will be used to test the changes of insomnia severity in two groups. Mixed model for repeated measures will also be used to test the secondary objectives with potential covariates in the model. Demographic, psychiatric, and/or drinking-related factors significantly related to the outcomes listed in the secondary objectives will be entered in the model. Aikake information criterion and the Bayesian information criterion will be used to select best-fitting models. A potential dosing effect analysis including the number of cores completed as a covariate will be conducted for the treatment group only. With the linear mixed model approach, all available data points will be included in the analyses. Under missing completely at random and missing at random assumptions, linear mixed model with restricted maximum likelihood estimation can produce unbiased estimators (Salim, Mackinnon et al. 2008).

Investigator Conflicts: NIH guidelines on conflict of interest have been distributed to all investigators. NIH guidelines on conflict of interest have been distributed to all investigators.

Technology Transfer: No technology transfer agreement is in place for this protocol.

4 Rationale for subject selection

This study will be open to both males and females of all racial and ethnic groups, without targeting any specific group. We anticipate the target enrollment of participants to reflect the racial/ethnic distribution of residents in the greater Washington DC metropolitan area.

5 Recruitment plan

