Clinical monitoring will be conducted in accordance with the Clinical Center (CC) Monitoring Policy. In brief, protocols will be submitted to the CC Quality Assurance Coordinator who will determine the frequency and complexity of monitoring based on the IRB assigned risk and patient populations. Monitoring will be performed by the CC Quality Assurance Coordinator.

Participants will be discontinued/withdrawn from the study if any of the following events occur: participant requests to be removed from study, participant is admitted to an addiction inpatient treatment program at the NIH or elsewhere within 9 weeks of discharge from 1SE (upon PI discretion), participant exhibits any condition which the MAI finds CBT-I to be a hazard to the participant (i.e. participant seems agitated, onset of increasing paranoia) participant is unable to comply with study-related procedures (i.e. SHUTi program recommendations and/or "homework), and/or participant develops a medical illness or condition that requires a new hospital admission.

10 Data/Records Management

The PI will be responsible for assuring that all investigators follow the plan for protecting the confidentiality of information and data provided by research participants. Assessments collected via paper-and-pencil questionnaires will be de-identified through the use of non-identifiable codes. The key to the code will be kept securely and separate from data and samples. Participant information will be

Protocol Number: 18-CC-0079

maintained in secured databases and computers in locked files and a locked office. Paper records will be maintained in locked files and a locked office. Access to samples and data will be limited to authorized study personnel. The PI will be responsible for overseeing entry of the data (quantitative and interview transcripts) into a password protected electronic system and ensuring data accuracy, consistency, and timeliness.

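### Relapse has no scoring rule for participants withdrawn after addiction readmission, so the relapse rate is likely to be biased low by an amount the plan cannot show

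*Combined protocol and SAP*

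**What the plan says.** - **Diary source.** Section 2.4 makes relapse a categorical secondary outcome taken from the daily diaries: "whether the participant reports any drinking post-discharge". On completeness it says: "Participants will be asked to complete at least five out of every seven days of daily sleep and symptom diaries". The Table of Measures lists diaries at pre-test, at 3-4 weeks and at post-test.
- **Follow-up source.** The same table lists a "Dichotomous Yes/No Relapse Assessment" at 6-7 months post-discharge, by visit or phone, with the TLFB given after a *yes*. Section 2.2 adds that, for participants who cannot return, "we will attempt to conduct the surveys and interview via phone".
- **Withdrawal.** One of the events in Section 9 that leads to withdrawal is: "participant is admitted to an addiction inpatient treatment program at the NIH or elsewhere within 9 weeks of discharge from 1SE (upon PI discretion"). Section 9 says nothing about later contact or outcome scoring.
- **Attrition.** Section 3 plans for "an estimated attrition rate of 40 percent". Section 2.5.3 calls the 40% conservative and sets it beside a drop-out rate of about 34% from an earlier CBT-I program.
- **Missing data.** Section 3 examines patterns of missingness and otherwise relies on a linear mixed model using available data under MCAR or MAR. Its only tool for two categorical variables is a chi-square.

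No section says which source defines relapse, or how a withdrawn or lost participant is classified.

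**The concern.** Most missing outcomes arise for reasons that may or may not bear on the result. Here a written withdrawal criterion is closely linked to the outcome. A person admitted to an addiction program within weeks of leaving the unit is among the likeliest to have relapsed, and the plan allows that person's removal well before the 6-7 month item.

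The outcome also comes to depend on the calendar and on discretion. An admission in week 8 can lead to withdrawal. One in week 10 does not meet this criterion, so that participant can still be asked the follow-up question and counted.

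The stated missing-data method does not repair this. A linear mixed model for repeated measures is not a method for one yes/no value per person, and MAR is doubtful when the reason for leaving is so close to the outcome. At stake are the reported relapse rate and, if the arms lose different numbers of people, the comparison between them.

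**Working it through.** **1. The plan's own figure.** Inputs from Section 3: 60 participants, 40% attrition, correlation 0.6, two-sided alpha 0.05, power 0.80.

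- SD of change, in SD units: √(2 × (1 − 0.6)) = 0.894
- Completers per arm: 60 × 0.6 / 2 = 18
- Detectable effect: (1.960 + 0.842) × 0.894 × √(2/18) = 0.835, against the stated 0.84

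The figure reproduces. The plan therefore expects 60 − 36 = 24 people, 12 per arm, without complete insomnia data. For relapse, 40% is an upper figure: a diary report of drinking before leaving already meets the definition, and phone follow-up will score some others.

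**2. Effect on the relapse rate.** The documents give no relapse rate, so everything from here is assumption. Let u be the unscored fraction, p the relapse rate in those observed and q the rate in those lost.

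- True rate = (1 − u)p + uq
- Complete-case rate = p
- Shortfall = u(q − p)

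With u = 0.40, p = 0.50 and q = 0.70, the true rate is 0.6 × 0.50 + 0.4 × 0.70 = 0.58. Complete cases give 0.50, a shortfall of 8 points. Shortfall in points over a range, with p = 50%:

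| Unscored | q = 50% | q = 60% | q = 70% | q = 90% |
|---|---|---|---|---|
| 10% | 0 | 1 | 2 | 4 |
| 20% | 0 | 2 | 4 | 8 |
| 40% | 0 | 4 | 8 | 16 |

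**3. Effect on the arm comparison.** Suppose true relapse is 58% in both arms and 70% in those lost. Observed rate = (0.58 − 0.70u)/(1 − u).

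- Attrition 45% vs 35%: 0.265/0.55 = 48% vs 0.335/0.65 = 52%
- Attrition 50% vs 30%: 0.23/0.50 = 46% vs 0.37/0.70 = 53%

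Under these assumptions the arm that loses more people looks more abstinent, with no true difference.

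**4. How far the choice of rule can move a result.** Take 5/18 vs 12/18 relapsed among those observed, and 12 missing per arm.

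- Complete cases: Fisher p = 0.044
- Missing equals relapse: 17/30 vs 24/30, p = 0.095
- Best/worst case: the risk difference runs from (12 − 17)/30 = −17 points to (24 − 5)/30 = +63 points

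A rule left open until the data are seen could settle whether the result is significant.

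**The case against.** The other side has several fair points.

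- **Silence scored as abstinence.** A reader might infer that someone who stops reporting has reported no drinking and so counts as not relapsed. The documents do not say this. Section 2.4 defines only what a *yes* is, the 6-7 month item needs an answer, and Section 3 works with available data. Dropping the unscored is the nearest reading. Any inflated false-positive rate worked out from silence-as-no would rest on a rule that the plan does not contain.
- **The 40%.** A reader might take it to include readmission withdrawals. Section 2.5.3 sets it beside a CBT-I program drop-out rate and does not mention readmission. Leaving the program is also not the same as having no relapse report.
- **Recovery of some leavers.** Earlier diary entries and the phone route will score some of them, and Section 9 does not say that data already collected are discarded.
- **No automatic arm difference.** If relapse among those observed is equal in the two arms, complete cases show no difference whatever the attrition split. The result in step 3 needs equal true rates and higher relapse in those lost.
- **Weight.** Relapse is one of many secondary outcomes in a pilot powered on insomnia severity.

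All of these stand, and they limit the size of the problem. None supplies a scoring rule for a participant withdrawn under Section 9, or removes the link between that criterion and the outcome.

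**Conclusion.** The point holds in limited form. Relapse rests on what participants report, a stated withdrawal criterion can remove likely relapsers before the follow-up item, and the only missing-data method is a linear model under MCAR/MAR. Following the plan can therefore take outcome-related cases out of the relapse result, and the rate is likely to be biased low.

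The direction rests on one assumption: that people lost relapse more often than people observed. The size cannot be known from the documents. The 50% against 58% and the 46% against 53% are illustrations under assumed rates, with 40% overall treated as an upper figure for the unscored. The documents do not support saying that four in ten participants will be counted as abstinent. The change should be made before relapse is analysed. The primary insomnia analysis is not affected by this point.

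**What to change.** In Sections 2.4 and 3:

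1. Name the sources and the window for relapse. Score *yes* if the diary, the follow-up item, the TLFB or a documented post-discharge admission for alcohol treatment shows drinking, including for people withdrawn under Section 9.
2. Score *no* only on a completed negative follow-up item with no contrary evidence. Treat everyone else as missing, never as *no*.
3. Analyse all randomized participants with a binary-outcome method, for example multiple imputation using baseline and post-discharge data.
4. Report missing-equals-relapse and best/worst-case results as sensitivity analyses only. Multiple imputation is still usually MAR-based, and missing-equals-relapse has its own artefact: with 50% observed relapse in both arms, attrition of 45% vs 35% gives 0.55 × 0.50 + 0.45 = 72.5% vs 0.65 × 0.50 + 0.35 = 67.5%.
5. State whether people withdrawn under Section 9 are still contacted for the 6-7 month item.

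The cost is a few sentences and a small amount of analysis. An admission that triggers Section 9 is known to the team. The documents do not say how admissions elsewhere are found, so some may stay missing. The reported relapse rate will probably be higher and its interval wider. Nothing here changes clinical care or the withdrawal criterion itself.
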